Version: 2.0 Date: 24APR2017

A Randomized, Double-Blind, Vehicle-Controlled, Parallel, Phase II Study to Evaluate Efficacy and Safety of BAC in Patient with Alzheimer's Disease or Vascular Dementia

NCT Number	NCT02886494
Document Version	V2.0
Document Date	24APR2017
Sponsor	Charsire Biotechnology Corp.

PROTOCOL SUMMARY

Version: 2.0

PROTOCOL SUMMARY
A Randomized, Double-Blind, Vehicle-Controlled, Parallel, Phase II Study to Evaluate Efficacy and Safety of BAC in Patient with Alzheimer's Disease or Vascular Dementia
BAC for Alzheimer's Disease or Vascular Dementia Phase II Study
BAC-02
Phase II
Charsire Biotechnology Corp.
To evaluate the efficacy and safety of BAC in patients with Alzheimer's disease or vascular dementia
Randomized, double-blind, vehicle-controlled, parallel study
Patient aged at least 40 years old in United States diagnosed with Alzheimer's disease or vascular dementia
The sample size is determined to be 45 versus 15 patients (3:1 ratio) for Treatment versus Control groups, 60 patients in total. To ensure the completion of 60 evaluable (per-protocol population) patients, around 75 patients will be recruited.
BAC (vapor fraction from seeds of Glycine max (L.) Merr . and composition thereof), topical application on external nasal skin, scalp, and neck, 2 times daily, 30g/day
During the treatment period, patients may continue to receive routinely used medications or treatments for Alzheimer's disease or vascular dementia.
Twelve weeks
Screening, Randomization (Baseline) Treatment (Weeks 2, 4, and 8 compared to Baseline), Final (Week 12)
In each study site, patients who meet all eligible requirements for entry into the study will be randomized and stratified into 1 of 2 dementia types (Alzheimer's disease and non- Alzheimer's disease) into treatment group or vehicle control group in 3:1 ratio as shown below:

Treatment Group:

BAC

Control Group:

Matched vehicle

Note: Dementia types (Alzheimer's disease and non- Alzheimer's disease) are classified as follows:

- 1. Alzheimer's disease: Alzheimer's disease according to the NIAAA criteria + "Mixed" dementia (possible Alzheimer's disease with cerebrovascular disease) according to the NIAAA criteria
- Non- Alzheimer's disease: Vascular dementia according to the NINDS-AIREN International Workshop criteria

Patients Inclusion Criteria

A patient is eligible for the study if all of the following apply:

- 1. With either gender aged at least 40 years old
- 2. With a diagnosis of one of the following disease
 - i. Vascular dementia according to the NINDS-AIREN International Workshop criteria or
 - ii. Alzheimer's disease according to the NIAAA criteria
 - iii. "Mixed" dementia (possible Alzheimer's disease with cerebrovascular disease) according to the NIAAA criteria

Note:

- a. NINDS-AIREN: National Institute of Neurological Disorders and Stroke and Association Internationale pour la Recherche et l'Enseignement en Neurosciences
- b. NIAAA: National Institute on Aging-Alzheimer's Association
- With mild-to-moderate dementia (score of the Mini-Mental State Examination (MMSE) defined as between 10 to 24 and score of ADAS-Cog as at least 12)
- 4. Able to communicate and understand cognitive testing instructions
- 5. Having a responsible caregiver who spends at least 4 hours daily with the patient. The caregiver will accompany the patient to all study visits, supervise administration of study drug, and be able to assess the patient's condition

Version: 2.0

Version: 2.0

Date: 24APR2017

6. Patients and the responsible caregiver willing and able to provide written informed consent form. Patients who lack capacity to consent must be in agreement with entering into the study and have a personal legally authorized representative giving written informed consent to their participation.

Patients Exclusion Criteria

Any patient meeting any of the exclusion criteria will be excluded from study participation.

- 1. With large vessel thrombosis (thrombotic stroke occurring in large arteries)
- 2. With radiological evidence of other brain disorders (subdural hematoma, post-traumatic / post-surgery)
- 3. With dementia caused by other brain diseases except Alzheimer's disease and vascular dementia (e.g. Parkinson's disease, demyelinated disease of the central nervous system, tumor, hydrocephalus, head injury, central nervous system infection including syphilis, acquired immune deficiency syndrome, etc.)
- 4. With clinical evidence of pulmonary, hepatic, gastrointestinal, metabolic, endocrine or other life threatening diseases judged by investigators not suitable to enter the study
- 5. With clinically unstable hypertension, diabetes mellitus, and cardiac disease for the last 3 months
- 6. Ever hospitalized for stroke or with acute coronary syndrome in the previous 3 months prior to screening
- 7. Drug or alcohol abuse within the previous 12 months of screening.
- 8. With one of the following abnormal laboratory parameters: hemoglobin < 10 mg/dL or platelet $< 100*10^9/\text{L}$; creatinine or total bilirubin more than 1.5 times the upper limit value; alanine aminotransferase (ALT), aspartate aminotransferase (AST), alkaline phosphates (ALP), γ -glutamyl transferase (γ -GT) more than 2 times the upper limit of normal, or thyroid-stimulating hormone (TSH) more than 2.5 times the upper limit value or less than the lower limit value of normal

- 9. With severe depression graded by Diagnostic and Statistical Manual of Mental Disorders, Fifth Edition (DSM-5) and Cornell Scale for Depression in Dementia (CSDD)
- 10. With any uncontrolled illness (including, but not limited to, any of the following: ongoing or active infection including hepatitis B, C, and HIV, active bleeding, symptomatic congestive heart failure, uncontrolled hypertension, unstable angina pectoris or, cardiac arrhythmia) judged by the investigator that entering the trial may be detrimental to the patient
- 11. With known or suspected hypersensitivity to any ingredients of study product and vehicle
- 12. Pregnant or lactating or premenopausal with childbearing potential but not taking reliable contraceptive method(s) during the study period

Note: Reliable contraceptive methods will consider as below:

- a. Established use of oral, injected or implanted hormonal methods of contraception > 3 months prior to baseline.
- b. Placement of an intrauterine device (IUD) or intrauterine system (IUS) > 3 months prior to baseline.
- c. Barrier methods of contraception: Condom or Occlusive cap (diaphragm or cervical/vault caps) with spermicidal foam/gel/film/cream/suppository
- d. Partner male sterilization (i.e., vasectomy) > 1 month of screening
- 13. Enrollment in any investigational drug trial within 4 weeks of screening visit
- 14. Experienced dosage increment of routinely use in drugs listed as follows within past three months before Screening visit
 - a. medications/treatments for Alzheimer's disease or vascular dementia
 - b. antipsychotic medications including but not limited to selective serotonin reuptake inhibitors (SSRIs), benzodiazepine (BZD)
 - c. Vitamin B12
 - d. drugs for thyroid disease

Version: 2.0

15. Current antiplatelet drug (antiaggregant) except dosage including but not limited to aspirin ≤ 100mg/day, clopidogrel ≤ 75mg/day, ticagrelor ≤ 180mg/day, dipyridamole ≤ 400mg/day

16. Caregivers who have psychotic symptoms, are imminently suicidal, have an unstable medical condition (e.g. recent heart attack, recent stroke, episodes of dizziness, fainting attacks) or significant orthopaedic problems.

Primary Endpoint

Efficacy:

Change in Alzheimer Disease Assessment Scale-cognitive (ADAScog) score at Week 12 visit compared to baseline

Secondary Endpoints

Efficacy:

- 1. Change in ADAS-cog score at all post treatment visits (except Week 12 visit) compared to baseline
- Clinician's Interview Based Impression of Change-Plus
 Caregiver Input (CIBIC-plus) score at all post treatment visits
- 3. Change in Alzheimer's Disease Cooperative Study Activities of Daily Living (ADCS-ADL) score at all post treatment visits compared to baseline
- 4. Change in MMSE score at all post treatment visits compared to baseline
- 5. Change in Neuropsychiatric Inventory (NPI) score at all post treatment visits compared to baseline

Safety:

- 1. Adverse event incidence
- 2. Change in physical examination results
- 3. Net change from baseline in laboratory test results
- 4. Net change from baseline in vital signs

Statistical Analysis

Analysis Population

Two data sets will be introduced for statistical analysis.

Intent-to-treat (ITT) population:

 All randomized patients who have received at least one dose study medication.

Per-protocol (PP) population:

Sponsor: Charsire Biotechnology Corp.

Version: 2.0

(Project Number: BAC-02) Date: 24APR2017

Version: 2.0

- A subset of ITT population
- Fulfill all inclusion and exclusion criteria
- Accumulatively dosed with at least 63 days of study drug and with at least 75% of dosing compliance during treatment period
- With ADAS-cog score evaluation at or after Week 8 visit
- Did not receive any prohibited treatment during the study

Efficacy endpoints will be analyzed on ITT and PP population. Demographics, baseline characteristics, and safety endpoints will be analyzed on ITT population. The conclusion of efficacy will be made according to the results of ITT population analysis.

Analyses

Demographics and baseline characteristics will be summarized for each group by using descriptive statistics.

The efficacy endpoints will be compared between the BAC group and vehicle group. The primary endpoint of this study is change in ADAS-cog score at Week 12 visit compared to baseline. The test will be performed by ANCOVA with treatment group and center as factor and with baseline score as covariate. Test treatment group will be declared superiority if the null hypothesis is rejected and improvement in ADAS-cog of test product group is greater than that of matched vehicle group.

As for secondary endpoints, change in ADAS-cog score at all post-treatment visits (except Week 12 visit) compared to baseline will be analyzed by ANCOVA with treatment group and center as factor and with baseline score as covariate. Same statistical analysis methods will be applied for other secondary endpoints such as changes in ADCS-ADL score, MMSE score, and NPI score at all post treatment visits compared to baseline. The CIBIC-plus score at all post treatment visits will be presented by transition table.

All treatment group comparisons will be conducted with significance level of 0.05, using 2-tailed tests.

For safety analyses, adverse events will be reported by treatment groups and by physiological systems as appropriate. Incidence of adverse events between treatments will be analyzed by CMH test.

Changes in physical examinations will be displayed for each individual system. Net changes from pre-treatment laboratory test results and vital signs will be analyzed by descriptive statistics.

All treatment group comparisons will be conducted with significance level of 0.05, using 2-tailed tests.

Additionally, descriptive statistics will be provided for all of the endpoints. Frequency table will be provided for categorical data, while mean, standard deviation, maximum, minimum, median, interquartile range (IQR), and 95% two-sided confidence interval will be calculated for continuous measurements.

Version: 2.0

SCHEDULE OF ASSESSMENTS

Visit	Screening	Randomization ¹ (Baseline)	Treatment		Final	
Visit No.	1	2	3	4	5	6
Weeks relative to Baseline visit	-2~0	0	2	4	8	12
Visit Window (days)	NA	NA	±4	±4	±4	±4
Informed consent signed and given	X					
Screening number assignment	X					
Randomization		X				
Demographic data & medical history	X					
Inclusion and exclusion criteria	X	X				
Pregnancy test for applicable patients	X					
Imaging (CT/MRI)	X ⁵					
ADAS-cog	X	X		X	X	X
CIBIS/CIBIC-plus ²		X		X	X	X
ADCS-ADL		X		X	X	X
MMSE	X	X		X	X	X
NPI		X		X	X	X
Vital signs	X	X	X	X	X	X
Physical examinations	X	X	X	X	X	X
Laboratory test	X^3	X^4				X
Record concomitant medication(s)	X	X	X	X	X	X
Record AE		X	X	X	X	X
Dispense trial medication		X	X	X	X	
Dispense Subject Diary		X	X	X	X	
Return trial medication			X	X	X	X
Return Subject Diary			X	X	X	X
Complete exit form						X
Dismiss patient						X

- 1. Can be on the same day of Screening visit if patient meets entry criteria
- 2. Randomization visit: CIBIS; Other Visits: CIBIC-plus
- 3. Laboratory test results within 7 days before Screening visit are acceptable.
- 4. Laboratory test results within 21 days before Randomization visit are acceptable and can be used as baseline measurement. If laboratory test results within past 21 days are not available, the laboratory test has to be performed.
- 5. Results of CT/MRI (computed tomography/ magnetic resonance imaging) obtained within 12 months before Screening visit are acceptable

Version: 2.0

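### The hemoglobin limit in exclusion criterion 8 is printed in mg/dL, 0.01 g/dL as written, so it excludes no patient if applied literally

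*Combined protocol and SAP*

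**What the plan says.** Criterion 8 under Patients Exclusion Criteria in the Protocol Summary lists laboratory abnormalities, any one of which excludes a patient. It opens: "With one of the following abnormal laboratory parameters: hemoglobin < 10 mg/dL or platelet". The remaining parts are a platelet count per litre and limits set against the laboratory's normal range, for example "creatinine or total bilirubin more than 1.5 times the upper limit value". The liver enzyme and TSH limits are also set against the normal range.

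The sentence introducing the exclusion list makes each criterion binding: "Any patient meeting any of the exclusion criteria will be excluded from study participation". The Schedule of Assessments has eligibility checked at both Screening and Randomization, and laboratory results are required for both visits.

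The criteria are used again in the analysis sets. Membership of the per-protocol (PP) population requires patients to "Fulfill all inclusion and exclusion criteria", and the recruitment target is counted in that population: "To ensure the completion of 60 evaluable (per-protocol population) patients, around 75 patients will be recruited". For efficacy, however, the plan states: "The conclusion of efficacy will be made according to the results of ITT population analysis".

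**The concern.** A limit of 10 mg/dL is far below any hemoglobin concentration compatible with life, so the hemoglobin part of criterion 8 does nothing as written. The sponsor evidently meant to set an objective lower bound, and the text does not set one.

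Two things are at stake. The first is screening. A patient with low hemoglobin is eligible on the text but may be turned away by a site that mentally corrects the unit, so sites could screen differently. The second is PP classification. If such a patient is enrolled, the person assigning analysis sets has only the printed limit, under which the patient qualifies, or an inferred limit, under which the patient does not. No written rule says which to use.

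**Working it through.** The limit is a stated threshold with no derivation behind it, so there is no plan figure to reproduce. The check is a unit conversion, a literal application of the criterion, and a search for a correction elsewhere.

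**Inputs**
- Printed limit: below 10 mg/dL (exclusion criterion 8).
- Range of patients' hemoglobin: not in the documents. Assumed 3 to 15 g/dL, with a wider range of 2 to 18 g/dL as a sensitivity check.

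**Conversion of the printed limit**
- 10 mg/dL ÷ 1,000 = 0.01 g/dL.
- 0.01 g/dL × 10 = 0.1 g/L.

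**Literal application**
- 3 g/dL = 3,000 mg/dL, and 3,000 ÷ 10 = 300 times the limit.
- 15 g/dL = 15,000 mg/dL, and 15,000 ÷ 10 = 1,500 times the limit.
- On the wider range, 2,000 ÷ 10 = 200 and 18,000 ÷ 10 = 1,800 times the limit.

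No value in either range falls below 10 mg/dL. Even the lowest assumed value is 200 times the limit, so the result does not depend on the exact range.

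**Would a change of unit alone repair it?** That depends on the unit chosen, and the documents do not say which was meant.
- Read as g/dL, the limit moves by 10 ÷ 0.01 = 1,000-fold.
- Read as g/L, it becomes 10 ÷ 10 = 1 g/dL, a 100-fold move (1 ÷ 0.01). That is still below both assumed minima (2 and 3 g/dL), so this part of the criterion would remain practically inoperative.

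The number and the unit therefore have to be settled as a pair.

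**Is it corrected elsewhere?** Hemoglobin appears nowhere else in the supplied text: there is no second statement of the limit, reference range or reporting unit. Two other exclusions offer a partial safeguard through investigator judgement. Criterion 4 covers "other life threatening diseases judged by investigators not suitable to enter the study", and criterion 10 covers uncontrolled illness "judged by the investigator that entering the trial may be detrimental to the patient". Neither gives a hemoglobin figure.

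**Effect on the analysis sets.** ITT consists of randomized patients who received at least one dose, so eligibility does not enter its definition. PP does depend on eligibility. Under the literal reading the hemoglobin limit removes nobody from PP; under an inferred, higher limit it could. The planned margin between recruitment and the PP target is 75 − 60 = 15 patients, or 15 ÷ 75 = 20%. That margin covers all causes of PP loss together, so it does not measure the effect of this error.

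**The case against.** The strongest reply is that this is an obvious slip in one unit with no demonstrated effect on any result. Sites would probably read g/dL. Criteria 4 and 10 let the investigator exclude an unsuitable patient, and criterion 10 is open-ended and names active bleeding. The efficacy conclusion rests on ITT, no endpoint uses a hemoglobin threshold, and laboratory changes are only described. Moreover, the printed limit can be applied to PP: everyone passes, so it cannot erode the target of 60. Finally, only the protocol summary and schedule were supplied; a fuller protocol, if there is one, may carry the right limit. A misread unit in the PDF text is also conceivable.

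Much of this stands. The primary test, the sample size and the ITT conclusion do not change, and the PP concern is limited to inconsistent reading, whose size cannot be derived. The statement that nothing corrects the limit holds only for the text supplied. The wording around the unit is intact and nothing suggests a reading error, but the source file should be checked.

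What does not stand is the inference that no correction is needed. A probable reading by sites is not a written criterion, and investigator judgement does not replace a numerical limit that the protocol set out to give. The text is an operative eligibility rule that is reused to define an analysis population, not background wording.

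**Conclusion.** The concern holds. As printed, the limit is 0.01 g/dL, and patients' values would exceed it by a factor of 300 to 1,500 (200 to 1,800 on the wider range), so the hemoglobin part of criterion 8 excludes no one. If 10 g/dL was meant, which is an assumption used only to size the error, the limit is out by a factor of 1,000. The rest of criterion 8 is unaffected.

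That no patient can have so low a value rests on general physiology rather than on the documents. The gap is too wide for the choice of range to matter. The likely consequence is uneven screening and uncertain PP membership for patients with low hemoglobin, not a change in the primary result. The point should be corrected, but it does not threaten the trial's conclusion. Confidence is high.

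**What to change.** The sponsor should check the limit against the source file and any fuller protocol. The medical lead should then confirm the intended number and unit together, since changing the unit alone may leave the limit inoperative. The confirmed pair should replace the present text in criterion 8 and be carried into any eligibility form (none was among the documents supplied) and into the eligibility check for PP, so that all sites and the PP review apply one written limit. No cut-off is proposed here; that is for the sponsor's medical lead.

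The cost is low: one corrected limit in the next protocol version, with matching edits to any form or check that repeats it. The sample size and the analysis methods do not change.

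### Does a per-protocol rule that accepts a Week 8 ADAS-cog score undermine the Week 12 primary analysis?

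*Combined protocol and SAP*

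**What the plan says.** Under Statistical Analysis, Analysis Population, the Protocol Summary sets two PP conditions that bear on timing. One concerns exposure: "Accumulatively dosed with at least 63 days of study drug and with at least 75% of dosing compliance during treatment period". The other concerns assessment: "With ADAS-cog score evaluation at or after Week 8 visit". Neither asks for a Week 12 score.

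Under Analyses, the endpoint is fixed at Week 12: "The primary endpoint of this study is change in ADAS-cog score at Week 12 visit compared to baseline". The sample-size paragraph counts patients on the PP set: "To ensure the completion of 60 evaluable (per-protocol population) patients, around 75 patients will be recruited".

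The populations have unequal roles. "Efficacy endpoints will be analyzed on ITT and PP population", but "The conclusion of efficacy will be made according to the results of ITT population analysis".

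The Schedule of Assessments places ADAS-cog at Screening, Baseline and Weeks 4, 8 and 12, with a window of ±4 days on each visit after Baseline. The row "Dispense trial medication" is last marked at Week 8, so dosing can continue after that visit. Study drug and diaries are returned at Weeks 2, 4, 8 and 12.

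**The concern.** A PP set is usually expected to hold patients who took the treatment as planned and supplied the endpoint. Here a patient can take drug past day 63, miss the Week 12 test, and still qualify on a Week 8 score. That score comes before the exposure floor could have been reached. Two things would seem to be at stake:

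- The 60 evaluable patients might not be 60 patients with a primary endpoint. With only 15 planned controls, a few missing control scores matter for precision.
- The PP Week 12 ANCOVA could be run on observed scores, with an N below the PP N, or with Week 8 scores standing in for Week 12. The supplied text does not say which.

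**Working it through.** **The plan's own figures.** Twelve weeks is 84 days, and 63/84 = 75%, so the two parts of the exposure rule agree. The step from 60 to 75 is consistent with a 20% loss: 15/75 = 20%, and 60/0.80 = 75. No loss rate is stated, and without an effect size, SD or power the 60 itself cannot be reproduced.

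**Timing.** Week 8 is day 56 ± 4, that is days 52 to 60. At most 60 days can have been dosed by then (61 if the Baseline day counts), which is below 63. Week 12 is day 84 ± 4, that is days 80 to 88. So there is a stretch, from the day 63 dosed days are reached until the Week 12 test, in which a patient can leave and still meet both PP conditions on a Week 8 score.

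**How many (assumptions, not document figures).** Let a share p leave by day 63 at a constant rate, h = −ln(1 − p)/63. This gives 0.00167 per day for p = 10% and 0.00354 for p = 20%. The 20% is high, because it treats the whole allowance as departures although PP also excludes for eligibility, compliance and prohibited treatment. With dosing on a fraction f of days, 63 dosed days are reached on day 63/f. Expected leavers = 60 × (1 − exp(−h × (D − 63/f))), floored at 0, where D is the day of the Week 12 test.

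| f | Day 63/f | p = 10%, D = 80 to 88 | p = 20%, D = 80 to 88 |
|---|---|---|---|
| 1.00 | 63 | 1.7 to 2.5 | 3.5 to 5.1 |
| 0.90 | 70 | 1.0 to 1.8 | 2.1 to 3.7 |
| 0.80 | 78.75 | 0.1 to 0.9 | 0.3 to 1.9 |
| 0.75 | 84 | 0 to 0.4 | 0 to 0.8 |

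Patients who finish dosing but miss the test would add to these counts, so they are not an upper limit.

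**Effect on the PP Week 12 analysis, observed scores only.** Compare two membership rules: the plan's, and one that requires a Week 12 score. The ANCOVA on observed Week 12 change uses patients who meet the other PP conditions and have a Week 12 score. That group is the same under both rules, so the estimate, standard error and p-value are identical. Against a full 45 versus 15, missing scores do cost precision:

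- four lost in proportion: sqrt(60/56) = 1.035, or 3.5%;
- four lost from control only: sqrt(1/45 + 1/11) / sqrt(1/45 + 1/15) = 0.336/0.298 = 1.128, or 12.8%.

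That cost comes from the missing tests. Rewording the membership rule does not recover it.

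**Effect if a Week 8 score stands in.** Assume the effect grows linearly, so that at Week 8 it is 56/84 = 2/3 of its Week 12 size. With k stand-ins spread in proportion, the dilution is (k/60) × (1 − 56/84). For k = 4 it is 2.2%, and for k = 5 it is 2.8%. If four were all on BAC, it is (4/45) × (1/3) = 3.0%.

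**ITT.** Membership requires randomization and one dose. The PP rule does not enter it.

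**The case for a change.** The strongest argument for a change is about sizing. The 60 is counted on the PP set, so the trial can reach its target while holding fewer Week 12 scores. If the design had 80% power (an assumption; none is stated), 45 versus 15 detects 0.835 SD. With 55 scores, power at that difference falls to about 77% (41 versus 14) or 75% (42 versus 13). Sixty Week 12 scores with a further 5% of PP patients lacking one would need 60/(0.80 × 0.95) = 79 recruits instead of 75.

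The arithmetic stands, but its reach is limited. Those power figures describe the PP analysis, which does not decide efficacy. ITT draws on all randomized and dosed patients from about 75, including some with a Week 12 score who fail PP for other reasons. The 75 is given as approximate, and four more recruits rest on an assumed rate.

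A second argument is that the supplied text leaves the stand-in question open. It does. But the text is a summary and a schedule, so the rule may be in the full statistical section. The question is also not particular to PP: a missing Week 12 score needs handling in ITT as well, and a sentence limited to PP would leave that untouched. It is a separate question from how PP membership is defined.

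The PP wording also has a sensible purpose. Efficacy is analyzed on PP at every visit with an assessment, and a Week 12 requirement would drop adherent patients from the Week 4 and Week 8 comparisons. Accepting a score after Week 8 leaves room for a late or early final assessment, which the summary neither describes nor excludes. Finally, because drug and diaries come back at visits, dosing after Week 8 is normally documented only at a later contact. This probably narrows the group further.

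**Conclusion.** The observation is accurate: PP membership does not require the Week 12 endpoint, and the documents do not bound how many such patients there could be. It does not call for a change. A PP set with a minimum exposure and a minimum assessment is a defensible choice, the two conditions do not conflict, and a PP N above the N at one visit is ordinary.

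With observed scores, the PP Week 12 result is the same under a stricter rule. With Week 8 stand-ins, the supportive estimate moves by about 3% or less for up to four patients, and by 2.8% for five spread in proportion, assuming linear growth of the effect. The illustrative count of about 0 to 5 of 60 rests on constant departure of 10% to 20% by day 63 and leaves out patients who complete dosing but miss the test. The ITT conclusion does not depend on the PP rule. Analysts would report the number of Week 12 scores by arm beside the PP result as a matter of course, and that shows the reader all that is at issue.

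### The summary gives no rule for ITT patients without a Week 12 ADAS-cog score, and the deciding ANCOVA leaves the Week 4 and 8 scores unused

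*Combined protocol and SAP*

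**What the plan says.** All of this is in the Protocol Summary, under Primary Endpoint, Secondary Endpoints and Statistical Analysis, and in the Schedule of Assessments.

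- **Who is analyzed.** ITT is "All randomized patients who have received at least one dose study medication". No post-baseline score is required. Both sets are used for efficacy ("Efficacy endpoints will be analyzed on ITT and PP population"), but ITT decides: "The conclusion of efficacy will be made according to the results of ITT population analysis".
- **What is tested.** The summary names a single visit: "The primary endpoint of this study is change in ADAS-cog score at Week 12 visit compared to baseline". For the method it specifies one model at that visit: "The test will be performed by ANCOVA with treatment group and center as factor and with baseline score as covariate". The model has no visit term.
- **Earlier scores.** The schedule has ADAS-cog at screening, baseline and Weeks 4, 8 and 12, and none at Week 2. The earlier post-baseline scores form a secondary endpoint: "change in ADAS-cog score at all post-treatment visits (except Week 12 visit) compared to baseline will be analyzed by ANCOVA".
- **Per-protocol criteria.** For dosing, the set needs "Accumulatively dosed with at least 63 days of study drug and with at least 75% of dosing compliance during treatment period". For scores, its requirement is "With ADAS-cog score evaluation at or after Week 8 visit".
- **Missing scores.** The posted text has no imputation or carry-forward rule, no complete-case statement, no repeated-measures model and no sensitivity analysis.

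**The concern.** A patient who takes one dose and leaves belongs to the set that decides efficacy but has no value for the test that decides it. The posted wording fits leaving such patients out, and it fits putting their last score in place of Week 12. These are different analyses. When loss is related to worsening in one arm only, they err in opposite directions, so neither is a safe default.

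Superiority rests on one test with about 19 vehicle patients, so a few missing scores can matter. The Week 4 and 8 scores would recover part of the lost information, but the primary test as written does not use them.

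**Working it through.** **1. Can a Week 12 score be missing within the plan's own sets?** In ITT, yes: one dose suffices. In the per-protocol set, treatment lasts 12 × 7 = 84 days, the dosing minimum is 63 days (63/84 = 75%, or 9 weeks), and Week 8 is day 56. A patient last scored at day 56 who doses to day 63 and leaves before Week 12 can therefore meet both criteria. The text allows this case.

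**2. The plan's own figures.** 60 × 3/4 = 45 and 60 × 1/4 = 15; 60 / (1 − 0.20) = 75. These agree with the stated 45, 15 and about 75. The 60 itself cannot be re-derived, because power, SD and effect are not given with it. The margin 1 − 60/75 = 20% is the planned per-protocol shortfall. It is not a Week 12 missing rate: per-protocol status can fail for other reasons, and a per-protocol patient may lack Week 12. I therefore assume 10% and 20% loss, which leaves 75 × 0.90 = 67.5 and 75 × 0.80 = 60 patients with a Week 12 score.

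**3. Assumed effect.** With 45 versus 15, two-sided 0.05 and 80% power, the detectable standardized difference is (1.960 + 0.842) × √(1/45 + 1/15) = 0.835, or 0.85 by the t test. At an assumed SD of 6 this is 0.85 × 6 = 5.1 points.

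**4. Simulation inputs.** From the documents: 75 patients at 3:1 (56 versus 19), the visits, the ANCOVA terms and alpha. Assumed:
- SD of change 6; correlations 0.65 (Weeks 4–8), 0.75 (8–12) and 0.55 (4–12)
- five centers of 15
- effect growing linearly to Week 12
- loss split equally after Week 4 and after Week 8
- score-driven loss at 1–2 logits per SD of the last observed change; in one-arm cases the other arm has random loss at the same rate

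The main runs had 8,192 trials per setting, with an unstructured Kenward-Roger mixed model for repeated measures (MMRM). Smaller check runs (1,500 to 4,000 trials) used a known-covariance model in place of the MMRM, where a repeated-measures model was run. Ranges cover the slopes and, where available, both sets of runs.

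**5. Results.** Pairs are 10% / 20% loss. Negative bias, in points, favors BAC. Nominal false superiority is 2.5%.

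| Setting | Dropping | Carry-forward | Repeated measures |
|---|---|---|---|
| Random loss, true −5.1: power | 84–86% / 78–81% | 84% / 79% | 86–87% / 83–85% |
| No effect, BAC leaves for worsening: bias | −0.4 to −0.6 / −0.7 to −1.1 | +0.2 to +0.3 / +0.3 to +0.5 | at most 0.04 |
| Same: false superiority | 4–6% / 6–10% | 1.4–1.9% / 0.9–1.6% | 1.7–3.2% |
| Same at 0.5 logits: false superiority | 3–4% / 4–5% | not given | not given |
| No effect, vehicle leaves for worsening: bias | +0.4 to +0.6 / +0.7 to +1.1 | −0.2 to −0.3 / −0.3 to −0.5 | at most 0.04 |
| Same: false superiority | 0.8–1.5% / 0.3–0.9% | 3.5–4.2% / 3.9–5.4% | 1.7–3.2% |
| No effect, one dropout rule in both arms: bias | none | none | none |
| BAC loss follows the unobserved next score: bias | −0.5 to −0.8 / −1.0 to −1.5 | −0.1 to −0.2 / −0.2 to −0.3 | −0.2 to −0.4 / −0.5 to −0.8 |

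Multiple imputation from Weeks 4 and 8 before the ANCOVA had bias of at most 0.02 when loss depended on observed scores, and power up to about 2 points below the MMRM.

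**6. Hand check of the dropping bias.** If a share m of the BAC arm is lost and would have ended D points worse than the arm's mean, dropping shifts the arm by −D × m / (1 − m). A shift of −0.9 at m = 0.20 means D = 0.9 × 0.80 / 0.20 = 3.6 points, or 3.6 / 6 = 0.6 SD. A shift of −0.5 at m = 0.10 means D = 0.5 × 0.90 / 0.10 = 4.5 points, or 0.75 SD. Whether leavers would differ that much is for the reader to judge.

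**7. Other SDs.** Bias in points scales with SD (5/6 = 0.83 at SD 5; 8/6 = 1.33 at SD 8). Error rates and power do not change, because loss and effect are set in SD units.

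**The case against.** **The posted text is only a summary and a visit schedule.** A rule may stand in a full protocol or SAP. This stands. A reader might infer that the efficacy conclusion hangs on an unwritten choice; the documents show only that the choice is not written in the summary.

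**A Week 12 ANCOVA adjusted for baseline and center is a standard primary analysis, and testing Weeks 4 and 8 as secondary endpoints is a design choice.** This also stands: the method is not an error. The case for change rests on its behavior with missing scores and on data already collected.

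**The per-protocol thresholds are minimums.** A patient who skips doses but attends Week 12 also fits them. So the plan allows a per-protocol patient without Week 12, but does not show that the sponsor expects one. The summary also does not say whether patients who stop treatment still attend Week 12.

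**The large error rates need score-driven loss in one arm.** Nothing in the documents supports that pattern. At 0.5 logits the inflation is small, and under a shared rule no method is biased without a drug effect.

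**Disagreement between methods is partly ordinary.** With random loss and a true effect, dropping and carry-forward gave different superiority verdicts in 7% / 12% of trials. A repeated-measures model also differed from dropping in 6% / 9%, and from the full-data ANCOVA in 5% / 9%. I do not rest the point on disagreement.

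**The MMRM is favored when loss depends on observed scores, because that is its own assumption.** True. The last row of the table shows it biased, and more so than carry-forward, when loss follows unobserved scores.

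**Conclusion.** The point holds as an improvement that should be made. It is not a fatal flaw. The summary lets a single-visit Week 12 ANCOVA on ITT decide efficacy, gives no rule for ITT patients who lack that score, and leaves the earlier scores out of the primary test.

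The size is conditional on the assumed inputs. With random loss, a repeated-measures model gains 1–2 power points at 10% loss and 4–5 at 20%, comparing methods within the same runs. With BAC loss driven by worsening and no drug effect, dropping gives false superiority of about 5% / 8%, carry-forward errs the other way, and the repeated-measures model is nearly unbiased if loss depends on observed scores.

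Two further readings go too far. The 20% recruitment margin is not a forecast of missing Week 12 scores. The trial's false-positive rate also cannot be said to be 5–8%, because that needs a loss pattern the documents do not describe. The omission itself depends on none of these figures. Confidence is medium, mainly because the full protocol or SAP was not available.

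**What to change.** 1. If the full protocol or SAP already fixes an adequate rule that uses the earlier scores, state it in the summary. Nothing more is then needed in the primary analysis.
2. Otherwise, make the primary analysis an MMRM of ADAS-cog change at Weeks 4, 8 and 12. Include treatment, visit, treatment-by-visit, center, baseline and baseline-by-visit, with unstructured covariance and Kenward-Roger degrees of freedom. The Week 12 treatment contrast is the primary test. Multiple imputation from Weeks 4 and 8 followed by the planned ANCOVA is an acceptable alternative.
3. Keep the observed-case ANCOVA as a sensitivity analysis, and add a delta-adjusted missing-not-at-random analysis that includes patients with no post-baseline score.
4. Report by arm the ITT patients with no Week 12 score and those with no post-baseline score.

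**Cost.** Wording and some programming; no new data or visits. The primary result would rely on missing-at-random and a covariance model. In the main runs its standard error was up to about 2% larger than by dropping (strong shared dropout rule, no drug effect) and about 7% larger than by carry-forward (20% random loss). Bias remains if loss follows unobserved scores. Patients lost before Week 4 are not recovered in the primary model. If a third of the loss came that early and BAC loss were score-driven, the MMRM bias was −0.1 to −0.2 / −0.2 to −0.3 points, against about 0 for carry-forward. The delta-adjusted analysis is there for these cases.
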